### **8.3. Subject Withdrawal Criteria**

An early termination occurs when a subject who provides written informed consent ceases participation in the study, regardless of circumstances, before the completion of the study. Subjects may voluntarily withdraw from the study at any time for any reason. In addition, the Investigator or the Medical Monitor may terminate a subject's study participation for reasons related to the best interest of the subject. Subjects who terminate from the study will not be replaced. Subjects may be terminated from the study due to any of the following reasons:

- Non-compliance
- Lack of efficacy
- Lost to follow-up
- Protocol violation
- Withdrawal by subject
- AE
- Death
- Other

If a subject is discontinued from the study before completing Month 12, then to the extent possible, all assessments, including safety, that are scheduled to be performed at Month 12 should be performed on the day of discontinuation.

[figure not shown]
Subjects who discontinue prematurely will not be replaced.

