## 3. STUDY DESIGN

### 3.1. General Study Design

This is a multicenter, open-label, extension study of intravitreal injections of the 440 µg dose of DE-109 in subjects with non-infectious uveitis of the posterior segment who received any dose of DE-109 and exited the SAKURA program under Santen Protocol 32-007. In addition, subjects who were randomized and received at least two injections of DE-109 during the first five months of the SAKURA study and obtained clinical benefit from the study medication, as determined by the Investigator, may be considered for entry in this 12-month extension study. The minimum time lag from last injection in the SAKURA program to entry into the SPRING program is 60 days. Any subjects can enter into protocol 32-009 US Amendment 01 if that subject is from U.S. and the time lag from exiting the SAKURA program to entry into protocol 32-009 is no more than 6 months.

Each subject retains the same subject ID as had been previously assigned in the SAKURA program. The study eye to be treated in this extension study is the same as the eye treated during the SAKURA program.

Study assessments are conducted for all subjects at Day 1 (Baseline), Month 2, Month 4, Month 6, Month 8, Month 10 and Month 12. Additional visits may be conducted according to the Investigator's standard clinical practice at interim unscheduled visits. DE-109 treatment may be administered in the study eye at the Investigator's discretion on Day 1 and/or any of the Post-Baseline PRN Treatment Visits at Month 2-10 but no more frequently than every 60 days. Treatment of the fellow eye with alternative local therapies is at the Investigator's discretion. However, administration of DE-109 to the fellow eye is a protocol deviation, and is counted as such.

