#### 4.1.3. Study Day / Days on Study / Days on Treatment

The *study day* variable describes the relative day of the observation starting with Day 1 as the reference date. There will be no Day 0. The study day will be calculated as follows:

- For events occurring on or after the reference date

$$\text{Study Day} = (\text{Date} - \text{Baseline Visit Date}) + 1$$

- For events occurring before the reference date

$$\text{Study Day} = (\text{Date} - \text{Baseline Visit Date})$$

*Days on Study* measures the duration each subject remains in the study and will be calculated as follows:

$$\text{Days on Study} = (\text{Study Exit Date} - \text{Baseline Visit Date}) + 1.$$

*Days on Treatment* measures the duration between the date of first exposure to DE-109 and exit date of each subject and will be calculated as follows:

$$\text{Days on Treatment} = (\text{Study Exit Date} - \text{Date of First Exposure to Treatment in SPRING Study}) + 1.$$

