## 4.4. Safety Related Definitions

### 4.4.1. Adverse Event

Under Protocol 32-009, an AE is defined as any *on-study* untoward medical occurrence (e.g. sign, symptom, disease, syndrome, intercurrent illness) that occurs in a study subject, regardless of the suspected cause and regardless of timing of DE-109 (440 µg) administration. An on-study AE can occur any time after the date of informed consent through the last study visit. An AE will be considered as *treatment-emergent* if the AE occurred on or after the date of the first DE-109 (440 µg) treatment in Spring Study up to the last study visit. Treatment-emergent AEs are a subset of on-study AEs.

The severity of each AE will be graded by the Clinical Investigator as Mild (aware or unaware of event, but easily tolerated), Moderate (discomfort enough to cause interference with usual activity), or Severe (incapacitating; unable to work or perform usual activity). Each AE will be classified into a system organ classification (SOC) and coded to a preferred term using Medical Dictionary for Regulatory Activities (MedDRA 16.0).

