## 6. GENERAL CONSIDERATIONS

All variables will be summarized by the last dose received in SAKURA study and overall. Continuous variables will be summarized using descriptive statistics such as number of observations (n), mean, standard deviation, medium, minimum, and maximum. Categorical variables will be tabulated using frequency (n) and percent (%).

All data manipulations and descriptive summaries will be performed using SAS Version 9.4 or later.

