#### **8.1. Adverse Event**

All AE(s) will be coded by MedDRA 16.0, 2013. All analysis will focus on on-study AEs given the PRN nature of this study. The information that whether an AE is treatment emergent or not

will be provided in all the AE related listings. All AE tables will be summarized by last dose received in SAKURA study, received injection or not in SPRING study, and overall.

Besides the overall summary of AEs, subjects with any AE(s) will be tabulated by SOC, preferred term, and maximum severity. A subject who experienced multiple AEs within a SOC or preferred term will be counted only once for that SOC or preferred term. SAEs, SARs, Serious SARs, study-medication related AEs, and injection-procedure related AEs will be tabulated similarly.

Ocular AEs, ocular SARs, serious ocular AEs, and serious ocular SARs will be summarized. Any ocular AE that occurred simultaneously to both eyes will be counted once for both the study eye and the fellow eye.

Sight-threatening AEs will be summarized by type of event specified in [Section 4.4.1.2.1](#).

Eye disorders AEs may be tabulated using lowest level term and preferred term to provide more detailed information.

Non-ocular AEs and serious non ocular AEs will be presented by SOC and preferred term.

All AEs reported during the study will be listed. SAEs, SARs, Ocular AEs, study-medication related AEs, injection-procedure related AEs, AEs leading to death, AEs leading to discontinuation, sight-threatening AEs, and ESIs, if any, will be listed separately.

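### The AE tables split subjects by injection status without showing time in study, so the columns can differ with no drug effect if some subjects leave early and some first injections come after Day 1

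*SAP*

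**What the plan says.** SAP section 8.1 sets the columns: "All AE tables will be summarized by last dose received in SAKURA study, received injection or not in SPRING study, and overall". The statistic is a count with a percentage; SAP section 6 says "Categorical variables will be tabulated using frequency (n) and percent". Repeated events do not add to the count: "A subject who experienced multiple AEs within a SOC or preferred term will be counted only once for that SOC or preferred term".

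The events are on-study AEs: "All analysis will focus on on-study AEs given the PRN nature of this study". Treatment-emergent status appears only in the listings. SAP section 4.4.1 fixes the observation period: "An on-study AE can occur any time after the date of informed consent through the last study visit". That period is shorter for anyone who leaves early. SAP section 4.1.2 provides for subjects seen only on Day 1, and Protocol section 8.3 says "Subjects who terminate from the study will not be replaced".

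Injection is at the Investigator's discretion. SAP section 3.1 allows it "on Day 1 and/or any of the Post-Baseline PRN Treatment Visits at Month 2-10", and SAP section 8.6 summarises time to first injection, so the plan expects that time to vary.

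SAP section 4.1.3 defines Days on Study, which "measures the duration each subject remains in the study and will be calculated as follows". No AE table uses it. Days on Treatment cannot replace it, because it starts at first exposure and has no value for a subject never injected.

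**The concern.** A column defined by something that happens after entry needs care when follow-up differs between subjects. A subject whose first injection would have come at Month 4, but who leaves at Month 2, is counted as non-injected with two months in which to report an AE. A similar subject who stays is counted as injected, with up to twelve. Unless all first injections fall on Day 1, the injected column therefore tends to hold longer follow-up, and longer follow-up gives a higher percentage with at least one AE at the same underlying rate.

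The sole objective is long-term safety, and a side-by-side table invites comparison. SAP section 7.1 summarises days to premature discontinuation, but the default grouping in SAP section 6 is last SAKURA dose and overall. A reader could not recover follow-up by injection status from the planned tables.

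**Working it through.** The plan has no figure to reproduce: it states no AE rate, dropout rate or injection timing, and SAP section 3.3 gives the sample size of 60 no statistical basis. The check asks what gap the planned tables would show with no drug effect.

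**Inputs, all assumed apart from the 360-day period (Month 12 is Day 360).** A share f is injected on Day 1. Of the rest, a share p would be injected by Month 12 if fully followed. Dropout by Month 12 is q. The 12-month AE risk is r, the same for everyone. Times to AE, dropout and first later injection are independent exponentials.

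**Formulas (time in units of 360 days).** Let d = −ln(1−q), i = −ln(1−p), a = −ln(1−r), and h(k) = (d/k)(1−e^−k) + e^−k. Among subjects not injected on Day 1:
- no injection before exit: h(d+i)
- neither injection nor AE before exit: h(d+i+a)
- no AE before exit: h(d+a)

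Then
- non-injected % = 1 − h(d+i+a)/h(d+i)
- injected % = {f[1−h(d+a)] + (1−f)[1−h(d+a)−h(d+i)+h(d+i+a)]} / {f + (1−f)[1−h(d+i)]}

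**Worked case: f = 50%, p = 60%, q = 20%, r = 60%.** d = 0.2231 and i = a = 0.9163. h(1.1394) = 0.4532 and h(2.0557) = 0.2227.
- Non-injected: 1 − 0.2227/0.4532 = 50.9%.
- Injected: (0.5×0.5468 + 0.5×0.3163)/(0.5 + 0.5×0.5468) = 0.4316/0.7734 = 55.8%.
- Gap: 4.9 points. Mean follow-up is 330 days injected and 297 days non-injected.

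**Range (gaps taken before rounding).**

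| f | p | q | r | Injected % | Non-injected % | Gap |
|---|---|---|---|---|---|---|
| 50% | 60% | 0% | 60% | 60.0 | 60.0 | 0.0 |
| 50% | 60% | 20% | 5% | 4.6 | 4.1 | 0.5 |
| 50% | 60% | 10% | 30% | 28.9 | 27.4 | 1.4 |
| 50% | 60% | 40% | 30% | 24.9 | 20.7 | 4.3 |
| 50% | 60% | 20% | 60% | 55.8 | 50.9 | 4.9 |
| 0% | 60% | 20% | 60% | 57.8 | 50.9 | 7.0 |
| 0% | 60% | 40% | 60% | 55.1 | 42.8 | 12.4 |
| 50% | 20% | 20% | 60% | 55.2 | 53.9 | 1.3 |
| 50% | 95% | 20% | 60% | 55.8 | 35.1 | 20.6 |
| 0% | 95% | 40% | 60% | 53.4 | 26.4 | 27.0 |

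If every first injection is on Day 1, then i = 0 and h(d) = 1. Both columns equal 1 − h(d+a), so the gap is zero. A simulation of the same model with 400,000 subjects per scenario agrees to within about 0.7 points.

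**Does person-time remove it?** At r = 60% the true rate is 0.9163 × 365.25/360 = 0.93 per subject-year. Simulated first-AE rates were 0.92–0.94 injected and 0.91–0.93 non-injected. With each subject's time divided at first injection they were 0.92–0.94 both before and after. Under a constant rate, expected total events are also proportional to time.

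**Does it matter which column holds the time?** Yes. In the simulation, about 16–19% of injected-column subjects with an AE had their first AE before any injection when half were injected on Day 1, and 45–50% when none were.

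**Sampling noise.** An injected share of 0.7734 splits 60 subjects about 46/14. The 95% half-width of the difference is 1.96 × √(0.558×0.442/46 + 0.509×0.491/14) = 0.30, or 30 points.

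**The case against.** The strongest reply is that the plan is descriptive, tests nothing and has 60 subjects. A 5-point artefact is less than one subject in a column of 14 (0.05 × 14 = 0.7), well inside the 30-point half-width. Early leaving is also visible: non-completers are listed, days to discontinuation and time to first injection are summarised, and AE listings carry the treatment-emergent flag. This stands as a limit on practical weight. It does not remove the problem, because a bias does not average out as noise does and none of those outputs shows follow-up for the columns being compared.

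Several stronger readings are tempting and should be resisted.
- A reader might infer that early leavers all fall in the non-injected column. They do not: an injection on Day 1 needs no follow-up, and an early leaver injected then stays in the injected column.
- A reader might infer that overall percentages are too low whenever subjects leave early. An AE is itself a listed withdrawal reason (Protocol section 8.3), and a subject who leaves because of one is already counted. The SAP does not call its percentage a 12-month risk.
- A reader might take a large gap from a one-sided example. At 1.0 AE per 360 days, full follow-up gives 1 − e^−1 = 63.2% and leaving at Day 60 gives 1 − e^(−60/360) = 15.4%. If one third of the non-injected leave then, that column reads 47.3%, 16 points below fully followed injected subjects. If one sixth of the injected leave too, their column reads 55.2% and the gap halves to 8.
- A reader might regard this split as the only contrast on current exposure. The SAP also plans changes after injection in IOP and ophthalmoscopy, and rescue rate by injection status.

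**Conclusion.** The point holds in a conditional form. The planned tables neither show nor adjust for time in study, and they use a column that can be settled after baseline. With both early withdrawal and first injection after Day 1, the columns can differ with no drug effect. The plan provides for both conditions but gives no rate for either, so the size is an assumption: most plausibly a few points, zero at the limits described, and above 20 points only where nearly all remaining subjects would eventually be injected. For rare events such as sight-threatening AEs the absolute gap is small (0.5 points at an assumed 5% risk).

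The direction is not assured either. The model takes withdrawal and injection as unrelated to AEs; withdrawal because of an AE, or injection prompted by active disease, could change it. This is a reporting weakness worth correcting because the correction is cheap, not a flaw that invalidates the safety evaluation.

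**What to change.** In SAP section 8.1, keep n (%) and show median Days on Study in each column. For all AEs, SAEs, ocular AEs, SARs and sight-threatening AEs, add number of events, subject-years and events per 100 subject-years, overall and by injection status. Subject-years are the sum of days divided by 365.25.

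For the injection-status rates, assign each subject's time and AEs before the first SPRING injection to 'not yet injected', and those from that date on to 'injected'. This matches the SAP's treatment-emergent rule. Rates by final column alone would leave pre-injection time and AEs under 'injected'. State how AEs with incomplete onset dates are placed, since SAP section 6.2.2 does not impute a completely missing date.

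The cost is SAP wording, some programming and slightly busier tables; no new data are needed. Rates will be unstable where subject-years are few, so subject-years should be printed beside each rate. Person-time corrects for unequal observation, not for the reasons why subjects were injected or withdrew, and a footnote should say so.

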## **8.2. Vitreous Haze (VH)**

VH score, change from baseline, and shift from baseline in VH at Month 12 visit and Study Exit visit will be summarized and listed.

Subgroup analysis will be performed for change from baseline in study eye at study exit by demographics and baseline characteristics in [Section 7.2](#).

Subjects with any score of 3+ or above in VH after Baseline will be listed.

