#### Ocular:

1. Active infectious uveitis. However, if the uveitis is the consequence of a previous infectious disease, such as tuberculosis, the previous infectious disease must be confirmed as no longer active.
2. Any implantable corticosteroid-eluting device (e.g. Ozurdex, I-vation, Iluvien, fluocinolone acetonide [FA] intravitreal implant) in the study eye:
  - a. If the Investigator confirms the device has no demonstrable efficacy as indicated in the package insert, the subject will be eligible
  - b. If a Medidur implant, Iluvien or Retisert has been implanted no less than 3 years and 90 days prior to Day 1, the subject will be eligible
  - c. If a Ozurdex implant, has been implanted no less than 180 days prior to Day 1, the subject will be eligible
3. Clinically suspected or confirmed central nervous system or ocular lymphoma
4. Progressive glaucoma which is unresponsive to treatment

5. Intraocular pressure of > 21 mmHg while on medical therapy, or chronic hypotony (<6 mmHg)
6. Any significant ocular disease that could compromise vision in the study eye. These include, but are not limited to:
  - a. Diabetic retinopathy: proliferative diabetic retinopathy (PDR) or non-proliferative diabetic retinopathy (NPDR) that compromise vision. Subjects with NPDR or PDR that does not compromise vision are not excluded from the study;
  - b. Wet age-related macular degeneration;
  - c. Myopic degeneration with active subfoveal choroidal neovascularization
7. Any of the following treatments to the study eye:
  - a. Intravitreal injections in the past 14 days
  - b. Intravitreal injections of DE-109 in the past 60 days
8. Ocular surgery within the past 30 days
9. Ocular or periocular infection in either eye
10. History of herpetic infection in the study eye or adnexa
11. Presence of known active, inactive toxoplasmosis or toxoplasmosis scar in either eye
12. Presence of any form of ocular malignancy in the either eye including choroidal melanoma
13. History of vitrectomy in the study eye

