### 4.2.3. Change from Baseline

The *change from baseline* in a measure at a post-baseline visit will be derived as:

Change from Baseline at a Post-Baseline Visit = (Score at the Post-Baseline Visit) – (Baseline Score).

For any measure assessed before and after injection at visits, only the pre-injection scores will be used to derive the change-from-baseline variable.

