**Table 3 Other Safety Assessments**

Safety Measures	Note
Slit-lamp Biomicroscopy: Vitreous haze	VH is assessed for each eye using the modified SUN scale as 0, 0.5+, 1+, 1.5+, 2+, 3+, or 4+. A decrease in VH score

	indicates improvement in the vitreous inflammation.
Best-corrected visual acuity	BCVA measures the acuteness or clearness of best-corrected vision in ETDRS letters (e.g., 75 letters). An increase in BCVA indicates improvement in the best-corrected vision. A 5-letter difference in visual acuity is equivalent to one Snellen line. A BCVA score of 85 ETDRS letters is equivalent to 20/20 vision, which is considered normal vision.
Intraocular pressure (IOP)	IOP, the fluid pressure inside the eye, is recorded in mmHg with one decimal point (e.g., 24.0 mmHg). If DE-109 is administered, a second assessment of IOP is made after injection.
Indirect ophthalmoscopy: lens and cataract	The lens of an eye is classified as Phakic, Aphakic, or Pseudophakic. Phakic lens is assessed for the presence of cataract (Yes or No).
Indirect ophthalmoscopy: Retina, macula, choroid, optic nerve	Retina, macula, choroid, and optic nerve, if able to be assessed, are graded as Normal or Abnormal. If DE-109 is administered, these ophthalmoscopy parameters are performed again after injection.
Slit-lamp biomicroscopy a : Lid Hyperemia, Lid Edema, Conjunctival Hyperemia, Chemosis, Corneal Edema, Conjunctival Discharge Exudate, Anterior Chamber Flare	The status of each of these biomicroscopy parameters is rated as 0 = None, 1 = Mild, 2 = Moderate, or 3 = Severe. For each abnormal record, the clinical significance (Clinically Significant or Not Clinically Significant) is also determined.
Slit-lamp biomicroscopy a : Pupil, Lashes, Ocular Motility, Iris	The status of each of these biomicroscopy parameters is determined as Normal or Abnormal. For each abnormal record, the clinical significance (Clinically Significant or Not Clinically Significant) is also determined.
Slit-lamp biomicroscopy a : Vitreous Cell Count	This measure is rated as 0 = 0 cells, 0.5+ = 1-10 cells, 1+ = 11-20 cells, 2+ = 21-30 cells, 3+ = 31-100 cells, or 4+ = $\geq 100$ cells.
Slit-lamp biomicroscopy a : Anterior Chamber Cell	This measure is rated as 0 = <1 cell, 0.5+ = 1-5 cells, 1+ = 6-15 cells, 2+ = 16-25 cells, 3+ = 26-50 cells, or 4+ = $\geq 50$ cells.

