## 4.5. Other Definitions

### 4.5.1. Rescue Therapy and Rescue Rate

*Rescue therapy* refers to any treatment that would have a therapeutic effect on the uveitis in the posterior segment (e.g., systemic treatment with an immunosuppressant agent, or a corticosteroid injection in the study eye) other than intravitreal DE-109. Topical ocular corticosteroid medication is not considered rescue therapy. Data related to rescue therapies will be reviewed and documented by the Medical Monitor prior to database lock to make the final determination of whether a medication will be classified as rescue therapy. *Rescue rate* is defined as the percentage of subjects who receive rescue therapy during the SPRING study among all subjects.

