## 6.2. Handling of Missing Data

### 6.2.1. Safety Measures

Descriptive summaries of safety measures will be based on observed data only. No imputation of missing scores will be implemented.

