### **8.7. Use of Rescue Therapy**

Subjects who take any medication qualified as rescue therapy, or who have vitrectomy procedures in study eye will be listed. The rescue rate in SPRING study will be calculated. Time to first rescue from Day 1 for rescued subjects will be summarized descriptively. Subgroup analysis of rescue rate will be performed by rescue status in SAKURA study, and received injection or not in SPRING study.

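### Vitreous haze recorded after a study-eye vitrectomy during SPRING enters the Month 12 and exit summaries unmarked, where a lower grade is read as improvement

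*SAP*

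**What the plan says.** SAP 8.2 plans the main VH output in one sentence: "VH score, change from baseline, and shift from baseline in VH at Month 12 visit and Study Exit visit will be summarized and listed". It adds subgroup summaries of change at exit by demographics and baseline characteristics, and a listing of subjects with any post-baseline grade of 3+ or more.

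Three general rules decide which values enter. SAP 6.2.1: "Descriptive summaries of safety measures will be based on observed data only". SAP 4.2.3, for measures taken before and after an injection: "only the pre-injection scores will be used to derive the change-from-baseline variable". SAP 5.1 keeps every enrolled subject with any safety data, injected in SPRING or not. SAP Table 3 says that a decrease in the score "indicates improvement in the vitreous inflammation".

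Vitrectomy appears in two places. Protocol 8.2, exclusion 13, bars study eyes with it at entry: "History of vitrectomy in the study eye". SAP 8.7 provides for it during the study, by listing only: "Subjects who take any medication qualified as rescue therapy, or who have vitrectomy procedures in study eye will be listed".

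Protocol 21.4.6 grades VH from 0 to 4+ by how blurred the optic nerve head and retinal vessels look to the examiner. VH is a named safety parameter (Protocol 14.1.1) and the only measure named for exploring efficacy (Protocol 11, SAP 4.3).

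**The concern.** The VH grade describes what can be seen through the vitreous. Vitrectomy removes that tissue, so a later grade may say more about the surgery than about the uveitis. If an eye worsened, was operated on and then graded low at exit, the plan would enter that grade as an ordinary observed value. In the mean change and the shift table the eye would look unchanged or improved, and nothing in the table would mark it.

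At stake is how the one measure that serves both as a safety parameter and as the efficacy exploration is read, in a study of 60 subjects whose tables are further split by last SAKURA dose (SAP 6).

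**Working it through.** **Inputs**

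- n = 60 (SAP 3.3), of whom 13 consented to US Amendment 01, leaving 60 - 13 = 47 outside it.
- VH scale 0, 0.5+, 1+, 1.5+, 2+, 3+, 4+ (Protocol 21.4.6). Change is the later score minus the Day 1 score (SAP 4.2.3).
- Not given: the number of vitrectomies, the baseline VH distribution, the expected mean change, and the split by last SAKURA dose. Values used for these below are assumptions.
- There is no sample-size or precision figure to reproduce: Protocol 14.1.2 and 14.1.3 give n no statistical basis and define no hypothesis.

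**Step 1. Does any rule keep these values out or mark them?** The observed-data rule admits them. The change-from-baseline rule concerns injections, not surgery. The population rule removes nobody for surgery. Tables are split by last SAKURA dose, and VH subgroups by baseline factors. Vitrectomy is not a named withdrawal reason (Protocol 8.3), so a subject can stay to Month 12. The exit visit is Month 12 or early termination, failing which the last visit (SAP 4.1.2), so the post-surgical grade is the one likely to be used. The answer is no.

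**Step 2. Would other outputs reveal it?** The 8.7 listing names the subjects, but the tables do not refer to it. The 3+ listing depends on a grade having been recorded. The scheduled Month 2 to 10 visits belong to US Amendment 01 only (SAP Table 1, footnote h). For the other 47 subjects, VH is required at Day 1, at injection visits, and at Month 12 or early termination; routine follow-up visits are not study visits (Protocol 9.3). A flare that led to surgery may leave no recorded grade.

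**Step 3. Contribution of one eye, compared with no change.** For an eye that ends at 0, contribution to the mean = -(baseline)/60.

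| Baseline VH (assumed) | Change | Contribution to mean | Share with lower VH |
|---|---|---|---|
| 0 | 0 | 0 | 0 |
| 0.5+ | -0.5 | -0.008 | 1/60 = 1.7 points |
| 2+ | -2 | -2/60 = -0.033 | 1.7 points |
| 3+ | -3 | -3/60 = -0.050 | 1.7 points |

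A baseline of 4+, the top of the scale, would give -4/60 = -0.067. One eye weighs more in a smaller column: in an assumed column of 20, -3/20 = -0.15 and 1/20 = 5.0 points.

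**Step 4. Effect of setting one eye aside.** Let c be its change and m the mean change of the other 59. The full mean is (59m + c)/60 and the mean without the eye is m, so the difference is (c - m)/60.

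- Assume m = -0.5 and c = -2: (-2 + 0.5)/60 = -0.025. The eye makes the full mean look better.
- Assume m = -0.5 and c = 0 (baseline 0, flare, surgery, exit 0): 0.5/60 = +0.008. The eye makes the full mean look slightly worse, although its flare is still hidden.
- For the share with lower VH, one eye that ends lower adds (1 - p)/60, where p is the share among the others. At an assumed p = 40%, that is 0.6/60 = 1.0 point.

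**Step 5. Chance that the issue arises at all.** P(at least one in 60) = 1 - (1 - r)^60. At assumed rates r of 1%, 2% and 5% this is 45%, 70% and 95%.

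**The case against.** The strongest reply is that this is small, traceable and uncertain in direction. Much of that stands.

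- **Direction.** A reader might infer a one-way bias in favour of DE-109. The documents do not support that. They nowhere say what vitrectomy does to the grade; that is inferred from the procedure. Nor do they equate vitrectomy with treatment failure. Retinal detachment and endophthalmitis are listed sight-threatening events (Protocol 12.1.3), and surgery for a complication would have no fixed direction for exit VH.
- **Size.** A fall of two or three grades needs a baseline of 2+ or 3+. Entry requires clinical benefit as judged by the investigator (Protocol 8.1, item 4), and no baseline distribution is given, so low baselines are plausible and the contribution may be close to 0.
- **Expectation.** A reader might also infer that the sponsor expects vitrectomies. SAP 8.7 only provides for listing them.
- **Attribution.** The tables include subjects never injected in SPRING and define no 'improved' category. Any improvement is read from negative changes and downward shifts, so it cannot be called improvement on DE-109.
- **Tracing.** VH values, vitrectomised subjects and ocular adverse events are all listed, so a careful reader can find the eyes by hand. This softens the problem but leaves the summary tables unmarked.
- **Selectivity.** VH after rescue medication also enters as observed. That is a related gap, but it concerns what a fall is attributed to; after vitrectomy the doubt is whether the grade still measures inflammation. A split by rescue might not isolate these eyes anyway: SAP 4.5.1 frames the pre-lock review as one "to make the final determination of whether a medication will be classified as rescue therapy", while 8.7 names vitrectomy separately.
- **Exclusion.** Dropping these eyes from the main table would be an exclusion that depends on outcome, and could itself flatter the result. This stands in full and shapes the remedy.

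**Conclusion.** The gap is real and modest. The SAP provides for study-eye vitrectomy during SPRING, admits the later VH grade to the mean, shift and subgroup summaries without a mark, and reads a fall as improvement. An operated eye that had worsened could therefore pass as unchanged or improved.

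The size is unknown, and zero if no study eye is vitrectomised. On the assumed 60 eyes, and compared with no change, each such eye contributes 0 to -0.05 to the mean change (baseline 0 to 3+, exit 0) and at most 1.7 percentage points to the share with lower VH. Setting an eye aside changes the mean by (1/60) x (its change minus the mean of the others), which can go either way. These figures rest on the inference that vitrectomy clears the graded view, and on every subject having a VH value.

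The documents do not support saying that the VH result is biased towards DE-109, or that these eyes should be removed from the main analysis. They do support asking that the eyes be visible in a descriptive table with no hypothesis test behind it.

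**What to change.** Keep the planned as-observed VH table for the full Safety Population. Before database lock, add to SAP 8.2:

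1. A separate row or shift category for study eyes vitrectomised during SPRING. It gives the number of eyes, baseline VH, last VH before vitrectomy with its date, and exit VH. The date matters because the last earlier grade may be the Day 1 value. These eyes are then not counted among those with lower VH without being visible.
2. A repeat of the mean-change and shift summaries without post-vitrectomy values, labelled as supportive.

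Flag the same eyes in the BCVA table (SAP 8.3).

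The cost is one row and one repeat table; the subjects must already be identified for the SAP 8.7 listing. The repeat table leaves out possible treatment failures, so it must not replace the main table or appear without the row. Settling this before lock avoids a choice made after the results are known.
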